4.4.6 RECRUITMENT EVALUATION PLAN

Using the recruitment database, each clinical site will track all relevant screening inclusion/exclusion data to enable the comparative evaluation of site-specific recruitment strategies, to monitor recruitment progress trial-wide, and to adapt strategies for recruitment where indicated. The primary measure of “success” will be the number of participants effectively enrolled at each clinical site.

4.5 PARTICIPANT WITHDRAWAL

Participants may withdraw informed consent at any time during the trial, personally or through their designated representative.

The clinical site Principal Investigator must document the reason for withdrawal of any participant from trial participation (see MOP for documentation tool).

4.6 PERMISSION TO EXTEND TRIAL FOLLOW-UP

As part of the initial informed consent, participants will be asked to consent for future contact according to national regulatory requirements.

5 INTERVENTION

5.1 INTERVENTION DESCRIPTION

The MACH15 Trial will include two intervention arms: one will assign participants to consume a moderate daily amount of alcohol defined as ~15 g (a standard U.S. serving) and the other will assign participants to abstain from alcohol. Because standard units of alcohol vary between countries, to ensure uniformity, clinical sites will convert ~15 g of alcohol to the standard unit for their localities. This comparison represents a clinical scenario in which a moderate amount of alcohol is ‘recommended’ by a clinician for potential health benefits. The intervention will average 6 years in duration, with a common participant close-out date. Although the beverage choice of participants will be actively and repeatedly monitored, participants in the alcohol arm can choose to consume beer, wine, or spirits. There is no clear evidence that any one beverage is preferable, and this approach both mimics usual drinking patterns and offers the greatest opportunity for long-term adherence.

The intensity of intervention will be similar in both arms of the trial, except for the assignment to consume or not consume alcoholic beverages. Promotion of adherence will be an important goal throughout the trial. Continuous feedback and discussions of challenges and solutions will take place between clinical site staff (e.g., health coach, dieticians), coordinators and participants. Adherence assessments will be performed during in-person visits, phone visits, and via individualized automated participant contacts (e.g., smart phone application, email, text messages) at varying frequencies throughout the trial (see Section 5.4.2). Participants in the alcohol arm will receive adherence counseling if they fall below 85% adherence (more than 4 non-adherent days per month) while those in the abstention arm will receive counseling if they fall below 100% adherence.

5.2 INTERVENTION DELIVERY PLAN

Due to the regulatory differences in alcohol sales between states, countries, and regions, clinical sites will have flexibility in terms of providing reimbursement for or distribution of alcohol. The clinical sites will propose various models for facilitating participants’ receipt of a monthly (or other period) supply of alcohol and the degree of success for each model will be reported to and monitored by the Intervention Subcommittee. Alcohol dispensing to participants will be adjusted as needed to facilitate best adherence and, based on experience with successful models, shared among the clinical sites. The reimbursement for or distribution of alcohol will be directly tied to the participant’s adherence to the protocol and responsiveness to regular contacts, which will provide additional protection from escalation in use. A more detailed description of the options for distribution of or reimbursement for alcohol will be provided in the Manual of Procedures (MOP).

Because most participants will incur increased costs if asked to drink daily, a compensation limit has been set equal to the monthly cost of the most commonly consumed alcoholic beverage in the region, depending upon prevailing policies and regulations at the clinical sites. The amount of the reimbursement will not be so large as to influence informed consent. Sites will have discretion regarding

whether to provide remuneration, reimbursement for or provision of nonalcoholic beverages for the abstinence arm.

5.2.1 ALCOHOL ARM

Participants in the alcohol arm will consume one U.S. serving (~15 g) of wine, beer or spirits daily for approximately 6 years. They will be asked to consume alcohol only after activities that require dexterity and alertness are completed for the day (i.e., at night) and will be advised to consume alcohol as part of a healthy diet.

5.2.2 ABSTENTION ARM

Participants in the abstinence arm will abstain from drinking alcohol for approximately 6 years. Complete abstinence is recommended to ensure sharp contrast between the two trial arms; however, a modest degree of tolerance towards alcohol consumption in the abstinence arm will be allowed. Participants may consume a limited number of alcoholic beverages at their discretion on special occasions. This will be monitored by site staff to ensure that adherence to the protocol is not compromised.

5.3 DIET AND LIFESTYLE FACTORS

Healthy dietary habits and lifestyle will be recommended to all participants for the duration of the trial, independently of the arm to which they are randomized. All participants will be given general advice and will be encouraged to follow a healthy diet, tailored to local recommendations.

5.4 INTERVENTION ADHERENCE

Adherence to the intervention regimens is necessary to the success of MACH15. All participants will be well-informed prior to entering the trial about the importance of adhering to their assigned intervention and that adherence will be routinely monitored.

5.4.1 RUN-IN (OPTIONAL)/WASHOUT PERIOD

Prior to randomization, individuals meeting all eligibility criteria will complete a two-week period during which they are to abstain from drinking alcohol. This will assist prospective participants with understanding their ability and willingness to comply with lifestyle changes regarding alcohol consumption. This also provides a brief washout period prior to baseline biospecimen collection.

Some clinical sites may choose to institute a run-in period prior to the washout during which prospective participants are to consume 1 drink (~15 g) of alcohol daily for 7 to 14 days.

Participants who successfully complete the two-week abstinence period (with or without an earlier optional run-in period of daily alcohol use) will be scheduled for their baseline randomization visit.

5.4.2 ADHERENCE MEASURES

Adherence to the intervention will be measured throughout the trial using a system of automated and in-person subjective and objective data collection tools. Participants will complete adherence assessments during each visit beginning at baseline and continuing until the trial ends. Collection of biological samples to monitor adherence will also occur during in-person clinic visits. Adherence assessments will also be completed during quarterly phone calls from clinical site staff.

In-person clinic visits will be supplemented by random, individualized automated participant contact via smart phone applications, email and/or text messages which will assess the number and types of drinks consumed in the prior 24 hours. Where automated, electronic contact is not feasible, brief phone calls from clinic staff to assess adherence will be performed. Participants will be periodically assessed for adherence via electronic means or phone calls at least 7 to 10 times every three months. Contact will be tailored to the participant's intervention arm and adherence profile, with greater intensity early in the trial, adjusting in frequency as needed based on individual compliance and responsiveness to contact.

5.4.2.1 OBJECTIVE BIOMARKERS OF ADHERENCE

Group adherence to the intervention will be assessed using High Density Lipoprotein Cholesterol (HDL-C) as an indirect biological marker. Additional more recently developed direct, objective biomarkers of adherence, especially urine biomarkers and hair samples may be used in all or a random sample of participants (see MOP for additional detail).

5.4.2.2 DATA COLLECTION INSTRUMENT

Contacts with clinical site staff may involve data collection on adherence to the intervention using the Timeline Followback (7 day) recall form and Yale-Brown Obsessive Compulsive Scale-heavy drinking (Y-BOCS-hd).

[figure not shown]
The Timeline Followback recall form asks participants to report the number of alcoholic drinks consumed each day in the previous 7-day period. The Y-BOCS-hd tracks changes in alcohol craving over time and will assist clinic staff in identifying participants at risk for developing problem drinking.

5.4.2.3 INDIVIDUALIZED AUTOMATED PARTICIPANT CONTACT

Throughout the trial, participants will receive brief electronic communications to assess and/or promote adherence. These automated contacts will occur at least 7 to 10 days each quarter and prompt participants to provide information on the amount and type of alcohol that was consumed in the prior 24 hours. Given the varied levels of familiarity and comfort with electronic communication, participants will choose their preferred method of communication (smart phone application, email or text message, or phone call) and may change their communication format at anytime during the trial. Clinical site staff will carefully monitor this system and, if the automated contact attempts are left unanswered or if adherence declines, they will initiate follow-up with an off-schedule phone call, as shown in Figure 5.1.

FIGURE 5.1: PARTICIPANT CONTACT

Methodology to detect non-adherent or unresponsive participants and subsequent steps.

5.4.3 INDIVIDUAL ADHERENCE COUNSELING

Specific steps to improve adherence will be established and explained in the MOP. Adherence problems may be identified by the participant via: 1) self-report; 2) comments about lack of adherence; or 3) stating he/she does not want to continue in the trial.

Participants with less than 85% adherence in the alcohol arm or 100% adherence in the abstinence arm or that drink excessively will receive adherence counseling by clinic staff using individualized motivational interviewing techniques (see Table 5.1). Such counseling will occur during each in-person clinic visit and phone visit and as needed based on responses to the adherence assessment measures. The participant will receive personalized advice directed to achieve ideal adherence to the protocol.

TABLE 5.1: TRIGGERS FOR ADHERENCE COUNSELING

Intervention Arm	Women	Men	Action
Daily Alcohol Low adherence (<85%)	No alcohol >1 day in 7 days of contact OR consumption of >1 alcoholic beverage >1 day in 7 days of contact	No alcohol >1 day in 7 days of contact OR consumption of >1 alcoholic beverage >1 day in 7 days of contact	Adherence counseling
Excessive alcohol consumption	>4 drinks on one occasion or >10 drinks in 7 days of contact	>5 drinks on one occasion or >14 drinks in 7 in days of contact	Intensive alcohol counseling
Abstention Low adherence (<100%)	Any alcohol consumption beyond or not in accordance with vouchers	Any alcohol consumption beyond or not in accordance with vouchers	Adherence counseling
Excessive alcohol consumption	>4 drinks on one occasion or >10 drinks in 7 days of contact	>5 drinks on one occasion or >14 drinks in 7 days of contact	Intensive alcohol counseling

The baseline visit will include formal counseling and motivational interviewing methods that have been used successfully in other clinical trials. They will be administered by a health coach, dietician, or similar professional trained during trial start-up and periodically refreshed via training during the trial. At each subsequent in-person clinic visit and phone visit, key concepts in maintaining adherence to the assigned intervention arm will be reiterated.¹⁻⁵

To maximize adherence, participants will be encouraged to bring spouses or significant others to clinic visits. This approach is explicitly recommended by www.clinicaltrials.gov and encourages spouses to act as trial partners, an approach that has been used in trials of other psychosocially-active interventions with some success.⁶

Additionally, clinical sites may provide health-related information and quarterly newsletters developed locally or centrally to reinforce the importance and value of each participant's role in the success of MACH15.

The Intervention & Adherence Subcommittee will collate and evaluate strategies to promote adherence to both study arms during the vanguard phase and will advise all clinical sites on their effectiveness to maximize trial-wide adherence during the subsequent study period.

6 TRIAL PROCEDURES AND SCHEDULE

6.1 TRIAL PROCEDURES/EVALUATIONS OVERVIEW

The data collection schedule for in-person clinic visits and phone visits in the MACH15 Trial is outlined in Table 6.1. Participant contacts include a prescreening phone call (optional) and an in-person screening visit aimed at determining eligibility for the trial. If eligible, participants will enter a run-in period (optional) and a 2-week washout period where they will be instructed to adhere to abstinence of alcohol. At the end of the washout period, participants will return to the clinic to complete the baseline trial assessments, randomization, and education regarding treatment assignment. Some clinical sites may choose to do the randomization and education on a separate day from the baseline assessments. In-person clinic visits will then occur at 3, 6, and 12 months, and every 12 months thereafter until close-out. Data may be collected over more than one day per participant preference. Phone calls for adherence counseling and ascertainment of safety and outcomes information will occur at 2 weeks, 4 weeks, 9 months, and every 3 months thereafter, except when the quarterly call falls at an annual in-person visit. Participants will have additional automated contacts (phone, email, text) related to adherence, described in *Chapter 5: Intervention*.

TABLE 6.1: MEASURES AND FREQUENCY

Contact Timeline:	Screening	Run-in (optional)/ Washout	Baseline/ Randomization ¹	2 & 4 weeks	3 & 6 months	9 months	12 months & Q12mos after	15 months & Q3mos after ²	90 months or Closeout
Contact Mode:	Visit	Call	Visit	Call	Visit	Call	Visit	Call	Visit
Measures									
Informed consent ³	X		X						
Contact information	X				X		X		X
Seated blood pressure and pulse	X		X		X		X		X
Weight			X				X		X
Waist circumference			X				X		X
Height			X						
Concomitant medications	X		X				X		X
Medical history	X								
Sociodemographics			X				X		X
Serious Adverse Events and MACH15 AEs				X	X	X	X	X	X
CVD outcomes				X	X	X	X	X	X
Lab-phlebotomy and processing	X		X		X		X		X
Genomic material			X ⁴						

Fasting glucose/ hemoglobin A1c	X ^{5,6}		X ⁷				X ⁷		X ⁷
AST/ALT/GGT	X		X		X		X		X
Creatinine	X								
HDL-C	X ⁵		X		X		X		X
Total cholesterol	X ⁵		X ⁸						
Triglyceride/LDL-C			X						
Blood storage			X				X ⁴		X ⁴
Urine storage			X ⁴				X ⁴		X ⁴
Hair clippings			X ⁴				X ⁴		X ⁴
Alcohol use questionnaires									
AUDIT	X								
Timeline Followback (7-day)	X			X	X	X	X	X	X
Y-BOCS-hd (3 items)	X				X		X		X
Other questionnaires									
Smoking History			X						
Fagerstrom Test of Nicotine Dependence			X				X		X
EQ-5D-5L			X				X		X
PHQ-9	X						X		X
Food Frequency Questionnaire			X ⁹				X ⁹		X ⁹
Physical Activity Measure			X ⁹				X ⁹		X ⁹
Verify eligibility			X						
Health Coaching									
Counseling on run-in (optional)/washout	X	X							
Behavioral and health counseling for intervention and adherence		X	X	X	X	X	X	X	

Abbreviations: mos = months; Q = every; CVD = cardiovascular disease; AST = aspartate aminotransferase; ALT = alanine transaminase; GGT = gamma-glutamyl transferase; HDL = high density lipoprotein; LDL = low density lipoprotein; AUDIT = Alcohol Use Disorders Identification Test; Y-BOCS-hd = Yale-Brown Obsessive Compulsive Scale-heavy drinking; PHQ-9 = Patient Health Questionnaire-9.

¹ Randomization and counseling for adherence may be done on same or different visit from Baseline Visit per site preference.

² Quarterly phone calls except when quarterly calls coincide with an annual in-person visit.

³ Separate informed consents may be obtained for collection and storage of samples to be used for genomic analyses and to collect alternate contact information where required by local regulations.

⁴ Optional annual collection per participant consent and/or clinical site ancillary studies.

⁵ If the participant has had these labs within 24 months, historical values may be used.

⁶ A self-report physician diagnosis of diabetes would be enough for screening and for determining the cardiovascular risk score (lab value is not required). However, if the participant does not know, either fasting glucose or HbA1c (non-fasting) should be used (historical values within 24 months may be used).

⁷ To assess for incident diabetes, all participants must have fasting glucose or HbA1c per clinic preference (fasting not required for HbA1c) drawn at the baseline visit and annually thereafter. If the value is above the ADA-defined cutoff for pre-diabetes, the participant will be asked to return to the clinic for a second blood draw to confirm the diagnosis. (Participants with known diabetes or that have been started on diabetes medication during the trial do not need to have a second blood draw.)

⁸ Does not need to be repeated if drawn at screening. If historical values were used to calculate AHA Risk Score, a baseline Total Cholesterol must be obtained.

⁹ Optional on-line questionnaires.

6.1.1 TRIAL SPECIFIC PROCEDURES

Inclusion and exclusion criteria are described in *Chapter 4: Participant Enrollment*. Additional trial specific procedures are described below and in the Manual of Procedures (MOP).

6.1.1.1 ANTHROPOMETRIC MEASURES

Anthropometric measures will be assessed using standardized methods at the baseline visit. Weight and waist circumference will be measured at each annual visit thereafter.

6.1.1.2 ALCOHOL USE MEASURES

The *Alcohol Use Disorders Identification Test (AUDIT)* is a 10-item questionnaire developed by the World Health Organization to assess alcohol consumption, drinking behaviors, and alcohol-related problems. It will be administered at the screening visit to identify and exclude participants with hazardous and harmful drinking habits or who may be alcohol dependent. Individuals who score above 5 on the AUDIT will be excluded from participation in the trial; this is conservative, below the recommended thresholds of 7-8.

Questions from the *Yale-Brown Obsessive Compulsive Scale-heavy drinking (Y-BOCS-hd)*; questions 7, 8, 10) will be administered at the screening visit, 3 month visit, 6 month visit, and annual visits thereafter to track changes in alcohol craving over time and to identify participants who may have developed problem drinking. Individuals who score is ≥ 6 at the screening visit, indicating moderate to severe cravings, will be excluded from participation in the trial.

6.1.1.3 BEHAVIORAL AND PSYCHOLOGICAL ASSESSMENTS

Current smoking status and history of smoking, including secondhand smoke exposure, will be assessed at the baseline visit. Nicotine dependence will be assessed at the baseline visit and each annual visit thereafter, using the *Fagerstrom Test of Nicotine Dependence*.

The *EQ-5D-5L™ (EuroQol-5 Dimensions-5 Levels)* is a self-administered, 5-item instrument applicable to a wide range of health conditions and treatments. It encompasses questions of mobility, self-care, usual activities, pain/discomfort and anxiety/depression and is designed to provide a single index value for health status. This commonly used measure of health utilities will convert quality of life and health

status into quality adjusted life-years (QALYs) for cost-effectiveness analysis. The EQ-5D-5L™ will be administered to all participants at the baseline visit and annually thereafter.

The *Patient Health Questionnaire-9 (PHQ-9)* is a self-report measure of depression that has been recommended by the American Heart Association (AHA) Advisory Panel on Depression and Coronary Heart Disease, has a low response burden (9 items, 2-3 minutes to complete), excellent reliability, and good sensitivity and specificity for diagnosing depression. This assessment will be completed at the screening visit and all annual visits thereafter. At screening, participants will be excluded who score ≥ 15 (moderate-severe depression) or indicate a positive response on question 9 dealing with suicide ideation. Information regarding alerts for elevated scores during the trial will be included in the MOP.

The *Food Frequency Questionnaire (FFQ)* consists of a finite list of foods and beverages with response categories to indicate usual frequency of consumption over the time period queried. This is an optional questionnaire that will be completed by participants following their baseline and annual visits.

The *Physical Activity Measure* is a self-report of time spent per week engaged in types of physical activity. This is an optional questionnaire that will be completed by participants following their baseline and annual visits.

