6.1.1.4 CLINICAL MEASURES

Seated blood pressure and pulse will be assessed in a standardized manner, after a 5-minute rest period using a standard automated device or, if necessary, a manual device. The preferred method is the automated device as it offers reduced potential for biases and decreased demand on staff in terms of training and effort in data collection. Three measures will be taken 1 minute apart and the average of the 3 measures will be obtained. Blood pressure and pulse will be collected at the screening visit, baseline visit, 3 month visit, 6 month visit, and all annual visits.

Concomitant medications are required to be recorded at screening, baseline and then reviewed and revised at annual follow-up visits. Prescription and non-prescription medication use will be collected and generic names will be recorded and entered in the database. Clinical sites may choose to collect information about medications more frequently. Participants will be asked to bring all medications to the screening, baseline, and annual visits. However, other appropriate sources for obtaining this information may also include current pharmacy action profiles, and/or verification of medications documented in the medical record.

Medical history is collected at screening to determine eligibility (see *Chapter 4: Participant Enrollment*). Data regarding presence of comorbidities are important for descriptive purposes, subgroup analyses and prognostic analyses. Clinical sites may supplement participant self-report with medical record information, if available.

Serious adverse events (SAEs) and selected adverse events (AEs), further referred to as MACH15 AEs, will be ascertained and reported during all participant visits (phone and in-person) beginning at the 2 week phone call. In addition, once participants have provided consent, any SAEs/MACH15 AEs that are

spontaneously reported by the participant or proxy at any time, or that are discovered in other ways are to be documented. Adverse event ascertainment and classification is described more fully in *Chapter 7: Assessment of Participant Safety*. Briefly, medical events and symptoms will be solicited at each visit, using a standard form that is administered by clinical site staff that may be unmasked to the intervention arm assignment. SAEs and MACH15 AEs will be reviewed at the clinical site by a masked clinician who will make the assessment as to relatedness.

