6.3.2 SCREENING

The in-person screening visit procedures include:

- Informed consent – Screening
- Contact information
- Medical history
- Concomitant medications
- Blood pressure and pulse
- AUDIT
- Y-BOCS-hd (3 items)
- Timeline Followback (7-day)
- PHQ-9
- Health Coaching (for adherence during washout)
- Blood draw for AST, ALT, GGT, and creatinine. Participants who have not had HDL, total cholesterol, in the prior 24 months will also need these at screening.
- A self-report physician diagnosis of diabetes is sufficient for the screening visit and for determining the cardiovascular risk score (lab value is not required). However, if the participant does not know, either fasting glucose or HbA1c (non-fasting) should be used (historical values within 24 months may be used).

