7.4.4 REPORTING OF PREGNANCY

The use of alcohol is a known risk factor during pregnancy. One of the main inclusion criteria in the trial is postmenopausal status. Therefore, women included in the trial will have a postmenopausal status and pregnancies are not expected to occur. However, if a pregnancy does occur, participation will be discontinued on the intervention.

7.4.5 INCIDENT CONDITIONS THAT RESULT IN PERMANENT OR TEMPORARY STOPPING OF ALCOHOL BUT CONTINUED FOLLOW-UP FOR OUTCOMES

The use of alcohol may be harmful in the following conditions. For this reason, the intervention will be discontinued at least temporarily in the following incident conditions (this list is not intended to be exhaustive):

- Dementia
- Heart failure Class III or IV
- Breast cancer
- Gastric bypass surgery
- Serious chronic liver disease (e.g., active hepatitis B and C infections) or liver tests (aspartate aminotransferase [AST], alanine aminotransferase [ALT] and gamma-glutamyl transpeptidase [GGT]) >2 times the upper limit of the normal range using local standards; GI bleeding.
- Estimated glomerular filtration rate (eGFR) drops to <30 ml/min /1.73m² or end-stage renal disease (ESRD)
- Ongoing use of any medication for which alcohol consumption is contraindicated
- A Patient Health Questionnaire (PHQ-9) score ≥15 or a positive response on question 9 dealing with suicide ideation
- Any organ transplant
- Pregnancy
- Development of alcohol use disorder

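### The PHQ-9 triggers a stop of alcohol but is not scheduled between randomization and month 12; adding it at the existing 3- and 6-month visits is a cheap safeguard

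*Combined protocol and SAP*

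**What the plan says.** Section 7.4.5 states that "the intervention will be discontinued at least temporarily in the following incident conditions", and one entry in its list is "A Patient Health Questionnaire (PHQ-9) score ≥15 or a positive response on question 9 dealing with suicide ideation". The same cutoff and the same item exclude people at entry (section 4.3, criterion 16).

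On timing, section 6.1.1.3 says: "This assessment will be completed at the screening visit and all annual visits thereafter". Table 6.1 agrees: the PHQ-9 is marked at screening, at annual visits and at close-out, and the column for 3 and 6 months is blank. An early termination visit can also include it (section 6.3.7). It is absent from the baseline list (6.3.5), the 3- and 6-month list (6.3.6.1) and both call lists (6.3.6.3 and 6.3.6.4).

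The 3- and 6-month visits already include blood pressure, liver tests, HDL-C, the 7-day Timeline Followback, the three Y-BOCS-hd items, coaching, and review of adverse events and CVD outcomes.

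Other provisions bear on detection:

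- Section 6.1.1.4: "medical events and symptoms will be solicited at each visit, using a standard form".
- Section 6.1.1.3, on the EQ-5D-5L, which has an anxiety/depression item: "will be administered to all participants at the baseline visit and annually thereafter".
- Section 6.1.1.3, on the PHQ-9: "Information regarding alerts for elevated scores during the trial will be included in the MOP".
- Section 7.4.3: depression and suicidality are not among the listed MACH15 AEs.

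**The concern.** The sponsor has decided that this state is incompatible with assigned alcohol, both at entry and during the trial, and has defined it by a score and a questionnaire item. In year 1 there are five scheduled staff contacts before month 12 (2 weeks, 4 weeks, 3, 6 and 9 months), and none is scheduled to yield either. An alcohol-arm participant who meets the condition after randomization, and whose symptoms do not surface another way, stays assigned to a daily drink until the month-12 form.

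Year 1 matters for two reasons. It is when assigned daily drinking begins, and section 4.2 admits people who have had as little as one drink in five years, so for some it is a large change. Section 1.2.4 itself links suicide attempts to acute intake, mainly heavy drinking but possibly lower doses too. Year 1 is also the only year with clinic visits between the annual ones, so an earlier form needs no new contact.

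The other routes are less structured. The symptom form, SAE reports and staff contact may prompt a check, but nothing in the protocol says that they produce a PHQ-9 score or a question 9 answer. Required medication review is annual (sites may do it more often), so a new antidepressant need not be recorded before month 12. The deferral to the MOP concerns what to do with a high score, not when to obtain one.

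**Working it through.** The plan gives no figure for this point, so the check is of the schedule, followed by the gain and the cost of the change.

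**1. Interval without a scheduled form.** After randomization, the longest scheduled interval in year 1 is now 12 months. With forms at 3, 6 and 12 months it is 6 months. Counted from the screening form, add at least the 14-day washout, and up to 58 days with a 14-day run-in, a 14-day washout and the 30-day goal for a split baseline. At 30.44 days per month that is 0.5 to 1.9 months. The gap to the first on-treatment form is then about 12.5-13.9 months now and 3.5-4.9 months after the change.

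**2. Mean wait from onset to the next scheduled form.** Assume that the condition persists until that form, and count scheduled forms only. For onset uniform over year 1, the mean wait is the sum of squared intervals divided by twice the total time.

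| Onset | Form at 12 only | Forms at 3, 6, 12 | Gain (months) |
|---|---|---|---|
| Uniform, months 0-12 | 12²/(2×12) = 6 | (3²+3²+6²)/(2×12) = 2.25 | 3.75 |
| Uniform, months 0-6 | 12 − 3 = 9 | 1.5 | 7.5 |
| Uniform, months 6-12 | 3 | 3 | 0 |

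Over six years with uniform onset, the mean falls only from 6.0 to (3²+3²+6²+5×12²)/(2×72) = 774/144 = 5.4 months, because the later 12-month intervals do not change.

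**3. Form burden.** Section 6.1.1.3 says that the PHQ-9 "has a low response burden (9 items, 2-3 minutes to complete".

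- Trial: 7,800 × 2 = 15,600 forms; at 2-3 minutes each, 520-780 participant-hours.
- Site of 500 (section 4.4.1): 1,000 forms, 33-50 hours.

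**4. Alerts and lost exposure.** The documents give no positive rate. Assume that 1-3% of the added forms meet the cutoff and that each alcohol-arm positive leads to a 3-month stop.

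- Alerts: 15,600 × 0.01 to 0.03 = 156-468 trial-wide, and 10-30 per site of 500.
- Alcohol arm: 3,900 × 2 × 0.01 to 0.03 = 78-234.
- Alcohol exposure lost: 78 × 0.25 = 19.5 to 234 × 0.25 = 58.5 person-years.
- Share of alcohol-arm time: 0.5-1.5% of year 1 (divide by 3,900), or 0.08-0.25% of planned follow-up (divide by 3,900 × 6 = 23,400).

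**5. Effect on power.** Section 8.2 assumes 10% non-adherence, so the effective hazard ratio is 1 − 0.18 × 0.90 = 0.838. With 3,900 per arm, 0.026 events per person-year in the abstention arm, 1% annual loss and follow-up uniform over 4.5-7.5 years, about 1,009 events are expected. Power is Φ(|ln 0.838| × √1,009/2 − 1.96) = Φ(0.85) = 80.2%, which reproduces the stated 80%. If non-adherence rose by a full point to 11%, the hazard ratio would be 0.8398 and power about 79.2%. The loss in step 4 is well below one point.

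**The case against.** The strongest reply is that nothing is broken. Section 7.4.5 lists conditions to act on when they come to notice; it is not a testing schedule. Other entries have less scheduled testing: creatinine, needed for eGFR, is drawn only at screening ("Blood draw for AST, ALT, GGT, and creatinine"), and no dementia instrument is scheduled. The list is expressly not exhaustive, and section 7.5 lets the site PI or the central safety monitors recommend stopping the intervention for an individual, so no score is needed to stop alcohol. Entry criteria already remove people at or above the cutoff and those with a history of alcohol or substance abuse. The evidence at lower doses is tentative, and nothing in the documents shows that onset clusters in year 1. The symptom form and the MOP are not available, so their content is unknown. Later 12-month gaps would remain. Form minutes are easy to count, but an alert on question 9 needs prompt clinical time that the documents do not cost.

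Most of this stands, and it is why the point is an improvement rather than an error. It does not remove the case for the change. The discretionary routes depend on someone noticing, and they do not replace the instrument that the sponsor chose for its own rule. Closing the eGFR or dementia gap would need a further laboratory test or a new instrument, whereas the PHQ-9 is already in use and the visits already take place. The annual forms already require a pathway for positive answers. If the positive rate exceeded 3%, the cost would rise, but so would the number of participants whom the sponsor's rule says should stop.

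**Conclusion.** The point holds as a recommended, low-cost safety improvement. It is not a statistical error, and the primary analysis is essentially unaffected. The gain is confined to year 1: 3.75 months in the mean wait under uniform onset, with a range of 0 to 7.5 months by timing. These figures assume persistence and no detection by another route; such detection would shorten the wait under both schedules. Without an incidence, the number of participants who would benefit is unknown. The lost alcohol exposure rests on the assumed 1-3% positive rate and 3-month stop, and is small against the 10% non-adherence already in the sample size.

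**What to change.** Add the PHQ-9 to the 3- and 6-month visits in Table 6.1, section 6.1.1.3 and section 6.3.6.1. Do so in both arms, so that ascertainment stays equal, and leave the stop condition in section 7.4.5 unchanged.

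The cost is two short forms per participant at visits that already take place, a small protocol and eCRF change, and clinical follow-up of the extra alerts. Sites should plan staff time for that follow-up, since it is the one cost that cannot be estimated from the documents. The change does not shorten the 12-month intervals in later years, where no clinic visit falls between the annual ones.
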